6.4.3.3 Correlation between SBP and Aldosterone

The correlation between SBP and aldosterone and will be explored by plotting change in office-measured SBP from baseline to Week 4 against 24hr urinalysis aldosterone levels at baseline for subjects randomized to 100 mg QD in Part 2 (the 'high-renin' cohort). Subjects will be grouped by race (African-American vs Non), with both race groups presented on the same plot.

The plot will be repeated for change in office-measured SBP from baseline to Week 4 against change in 24hr urinalysis aldosterone levels from baseline to Week 4, by race, for the same subjects.

6.5 Pharmacodynamics Evaluations

PD parameters (plasma 11-deoxycortisol, PRA, serum aldosterone, cortisol, and 11-deoxycorticosterone concentration) will be summarized descriptively in summary tables using observed values and change from baseline by treatment groups and scheduled visits. PD analyses will be performed using the PK/PD Analysis Set. A listing specifying PD samples not included in the summaries and reasons for exclusion will be provided.

6.6 Pharmacokinetic Evaluations

The analyses for the pharmacokinetic data will be described in a separate analysis plan.

6.7 Safety Evaluations

Safety analyses will use data from the Safety Analysis Set.

6.7.1 Adverse Events

Treatment-emergent AEs (TEAEs) are defined as AEs that occur at any point after the initiation of study drug (including placebo run-in period), or medical conditions present prior to the start of treatment but increase in severity or frequency following the initiation of the study drug up until 14 days following last dose of study drug.

On-treatment TEAEs during the double-blind treatment period will be further identified as those occurring or worsening after the initiation of randomized study drug.

AE marked as "Possibly Related" or "Definitely Related" will be summarized as being related to the study drug; otherwise, the AE will be considered unrelated to the study drug. If the relationship to

the study drug is missing, the event will be assigned as related to study drug. Missing severity will be summarized as separate category.

An overall AE summary will be presented by the number and percent of subjects in each treatment group and pooled active treatment group with the following:

- All AEs
- All TEAEs
- On-treatment TEAEs (during double-blind period)
- On-treatment Treatment-related TEAEs
- On-treatment TEAEs by worst severity (mild/moderate/severe)
- Serious TEAEs
- On-treatment Treatment-related serious TEAEs
- On-treatment Adverse Event of Special Interest (AESIs)
- On-treatment TEAE Leading to Withdrawal from Study Drug
- On-treatment TEAE Leading to Dose modification
- TEAEs leading to death

The following AE summaries will be produced by SOC and PT with the number and percent of subjects with the following:

- On-treatment TEAEs
- On-treatment TEAEs by severity
- On-treatment Treatment-related TEAEs
- Serious TEAEs
- On-treatment TEAEs leading to permanent withdrawal of study drug
- Fatal TEAEs
- On-treatment AESIs

The tables will display the counts and percentages of subjects who reported at least one AE in each SOC by treatment groups and pooled active treatment groups. Within each SOC, the tables will display the counts and percentages of subjects reporting at least one AE as designated by the PT. The outputs will be presented by descending frequency across all subjects for a given SOC and PT. At each level of summarization, a subject will be counted once if he/she reported one or more events. The severity and relationship to the study drug will be summarized in a similar manner. For example, if a subject reports multiple AEs of the same type, the subject will be represented in the most severe category or maximum relationship to the study drug.

The following AE listings will be prepared:

- All AEs
- On-treatment Treatment-related TEAEs
- Serious TEAEs
- On-treatment AESIs

- On-treatment TEAEs leading to permanent withdrawal of study drug
- On-treatment TEAEs leading to death
- All AEs reported during the run-in period

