### **8.3.1. Time Period and Frequency for Collecting AE and SAE Information**

All AEs and SAEs will be collected from Screening/start of Placebo Run-in (after signed Screening/main study ICF) until 30 days post last dose of study drug in Part 1 (Study Week 12) and 15 days post last dose of study drug in Part 2 (Study Week 10) at the timepoints specified in the SoA ([Table 1](#) and Table 2).

Adverse events that begin before the start of study drug, but after obtaining informed consent will not be considered treatment-emergent AEs. Adverse events collected during Placebo Run-in are considered treatment-emergent events.

All SAEs occurring from Screening/start of Placebo Run-in (after signed Screening/main study ICF) until 30 days post last dose of study drug in Part 1 (Study Week 12) and 15 days post last dose of study drug in Part 2 (Study Week 10) will be recorded and reported to the sponsor or designee immediately and under no circumstance should this exceed 24 hours. The investigator will submit any updated SAE data to the sponsor within 24 hours of it being available.

Investigators are not obligated to actively seek information on AEs or SAEs after conclusion of the study participation. However, if the investigator learns of any SAE, including a death, at any time after a subject has been discharged from the study, and he/she considers the event to be reasonably related to the study drug or study participation, the investigator must promptly notify the sponsor.

In the event that study drug is interrupted, AEs and SAEs will be collected throughout the interruption. If study drug is discontinued for any reason, the reason will be recorded and the subject should be encouraged to remain in the study so that important safety information can be obtained. All AEs and SAEs leading to discontinuation of study drug or discontinuation of study will be collected. Once a subject withdraws consent to participate in the study, no further information can be collected from the subject.

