4.1.4 Safety Analysis Set (SAF)

The Safety Analysis Set includes all enrolled subjects who received at least one dose of study treatment (MLS-101 or placebo). In analyses performed on the Safety Analysis Set, subjects will be analyzed according to their actual treatment received.

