6.2.6 Missing, Unused, and Spurious Data

Unless stated otherwise, missing data will not be replaced with imputed values. When relevant, sections below will address how missing data will be handled for the particular analyses.

Partial dates are allowed on the CRF for adverse events and concomitant medications. Only the day may be entered as unknown for the Adverse Event form while month and day may be entered as unknown for the Concomitant Medications (CM) form. Dates from these forms will be reported in listings as collected. Every effort will be made to query missing dates.

AEs will be flagged as on-treatment treatment emergent AEs (TEAEs) if the CRF question “Did this AE start prior to Randomization?” on the AE form is “No” regardless of whether or not the AE onset date is complete. AEs that cannot be definitively determined as occurring prior to study drug administration will be counted as TEAEs unless either the partial start date or a partial or complete end date indicates the AE as occurring prior to treatment. Partial dates entered in the AE form will be imputed for the purposes of determining whether the record is a treatment emergent adverse event or not based on the following:

- AE onset dates with missing day and non-missing month will be assumed to occur on the first day of the non-missing month, except for AEs occurring in the month and year of first dosing of study drug (including placebo run-in period), in which case the date will be imputed using the date of first dosing of study drug.
- AE onset dates with missing day and month will be assumed to occur on the first day of the non-missing year (i.e., January 1), except for AEs occurring in the year of first dosing of the study drug (including placebo run-in period), in which case the date will be imputed using the date of the first dosing of study drug.
- Partial or missing AE resolution dates will not be imputed.

Partial dates entered in the CM form will be imputed for the purposes of determining whether the record is a concomitant or prior medication based on the following:

- Medications that are not ongoing and have a medication stop date with a missing day and non-missing month will be assumed to occur on the last day of the non-missing month.
- Medications that are not ongoing and have a medication stop date with missing day and month will be assumed to occur on the last day of the non-missing year (i.e., December 31).
- Partial or missing CM start dates will not be imputed.

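### The by-arm serious TEAE tables count placebo run-in events under the later randomized treatment, because SAP 6.7.1 does not limit them to on-treatment events

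*SAP*

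**What the plan says.** **Start of the window.** SAP 6.7.1 counts as treatment-emergent all "AEs that occur at any point after the initiation of study drug (including placebo run-in period"). Protocol 8.3.1 likewise treats run-in events as treatment-emergent.

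**On-treatment subset.** The next paragraph of SAP 6.7.1 adds: "On-treatment TEAEs during the double-blind treatment period will be further identified as those occurring or worsening after the initiation of randomized study drug". Most rows and tables use this subset: TEAEs by SOC/PT, by severity, treatment-related, leading to withdrawal, and AESIs.

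**Rows without that limit.** "Serious TEAEs" appears in both the overall summary and the SOC/PT list with no on-treatment qualifier. So do the all-TEAE row, the row for TEAEs leading to death, and the fatal TEAE table. The listing of TEAEs leading to death is limited to on-treatment events.

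**Columns.** The tables show treatment groups and pooled active groups. Under SAP 4.1.4, safety subjects are placed by actual treatment received. No run-in column is planned, although run-in AEs have a separate listing.

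**End of the window.** The part of the definition about worsening of earlier conditions ends "following the initiation of the study drug up until 14 days following last dose of study drug". Protocol 8.3.1 collects AEs and SAEs "until 30 days post last dose of study drug in Part 1 (Study Week 12"), and for 15 days in Part 2.

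**Flag.** SAP 6.2.6 says "AEs will be flagged as on-treatment treatment emergent AEs (TEAEs) if the CRF question" on whether the event started before Randomization is answered No.

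**The concern.** The SAP separates run-in events from double-blind events and then leaves the separation out of the serious and fatal tables. In those tables a column headed with an MLS-101 dose can contain events that occurred before the subject took any MLS-101. If run-in events are equally common in all arms, they add the same background to every column and make a true excess on drug look smaller in relative terms. If by chance they fall unevenly, one event is a visible share of a small arm. The unclear end day and the two descriptions of on-treatment events add a further risk: two programmers working from the same SAP could produce different counts.

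**Working it through.** The documents give no figure for this point, so there is none to reproduce. The check compares the rules and then does window arithmetic.

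**1. Path of a run-in serious event.** Take a subject with a serious AE during the run-in who is later randomized to MLS-101 100 mg QD.
- TEAE under 6.7.1: yes, because it follows first study drug including run-in placebo.
- On-treatment TEAE: no, unless it worsens after the first randomized dose.
- Serious TEAE row and SOC/PT table: counted, because neither requires on-treatment status.
- Column: 100 mg QD, by actual treatment received.
- The neighbouring row for treatment-related serious TEAEs is limited to on-treatment events, so it would not count this event even if it were judged related.

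**2. Fatal events.** A subject who dies in the run-in is never randomized and has no drug column. Only an event with run-in onset and death after randomization can reach the fatal tables. The clearer fault is that the fatal table has no on-treatment limit while the listing of deaths does.

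**3. Weight of the run-in.** Inputs: run-in up to 14 days (Protocol 6.1.2), double-blind treatment 56 days.
- With a 14-day end: 14/(14+56+14) = 14/84 = 16.7% of the counting window.
- With 30 days (Part 1): 14/100 = 14.0%.
- With 15 days (Part 2): 14/85 = 16.5%.

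**4. Size per event.** Arms of about 30 (Protocol 4.1): 1/30 = 3.3 percentage points.

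**5. Illustration of dilution.** All risks here are assumptions; none is in the documents. Let the on-treatment SAE risk be 2% on placebo and 5% on drug, and let the run-in risk r be equal in all arms. Counted risk = 1 − (1 − p)(1 − r). The true ratio is 5/2 = 2.50.

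| r | Counted, drug | Counted, placebo | Ratio | P(at least one in 30) = 1 − (1 − r)^30 |
|---|---|---|---|---|
| 0.5% | 5.48% | 2.49% | 2.20 | 14% |
| 1% | 5.95% | 2.98% | 2.00 | 26% |
| 2% | 6.90% | 3.96% | 1.74 | 45% |

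The risk difference stays near 3 points throughout.

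**6. End day.** There are two readings of "up until 14 days following last dose of study drug".
- *It closes only the worsening clause.* No new event is lost, but a condition that worsens after day 14 is not a TEAE.
- *It covers all TEAEs.* Part 1 loses 30 − 14 = 16 of 30 collection days. With a last dose on Day 56, the Day 84 ± 3 visit falls 25 to 31 days after it, entirely outside the window. Part 2 loses 15 − 14 = 1 day.

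On either reading, the all-AE row and listing keep the late events.

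**7. The two on-treatment rules.** Both leave out an event that starts in the run-in and does not worsen. For an event that starts before Randomization and worsens after the first randomized dose, 6.7.1 counts it and the 6.2.6 flag makes no provision for it. The anchors also differ (Randomization against first randomized dose), but both fall on Study Day 1.

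**The case against.** The strongest reply is that the SAP follows the protocol: Protocol 8.3.1 itself calls run-in AEs treatment-emergent, and most AE tables are already on-treatment. Run-in events are listed separately, no formal safety testing is planned (Protocol 9.3.3), and nothing in the documents names the serious and fatal tables as the main safety comparison. All of that is correct. It does not answer the point, because calling an event treatment-emergent does not require showing it under a drug the subject had not yet received.

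On the flag, SAP 6.2.6 says *if*, not *only if*. Protocol 12.10.1 makes exacerbation of a pre-existing condition an AE, so a worsening might be entered with its own later start date. The CRF is not available to settle this. The fair statement is that 6.2.6 does not provide for worsening, not that it excludes it.

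A collection period also need not equal an emergence window, and a common 14-day end would give Parts 1 and 2 the same window. That is a legitimate choice if it is stated clearly and late serious events are still shown by arm.

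A reader might infer more from the safety set, defined as "all enrolled subjects who received at least one dose of study treatment (MLS-101 or placebo") without the word randomized, and conclude that subjects who took only run-in placebo join the placebo column. The documents do not support this. About 270 enter the run-in, about 160 qualify for enrollment, and the 160 enrolled are accounted for as 120 + 40 in randomized groups (Protocol 4.1). Protocol 5.4 classes subjects who are not randomized as screen failures.

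**Conclusion.** The point holds for serious events: as written, a serious run-in placebo event is counted in the later treatment column, including MLS-101 columns. The same applies to the all-TEAE row. For the fatal tables it holds only for run-in onset with death after randomization.

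One event is about 3.3 percentage points in an arm of 30. Dilution of the risk ratio is toward 1. Its size cannot be taken from the documents, and the illustration rests wholly on assumed risks that are equal across arms.

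The end day and the 6.2.6 flag are secondary. It would be tempting to say that the SAP drops every event after day 14, or that 6.2.6 contradicts the TEAE definition. Neither is established. The 14-day phrase may apply to worsened conditions only, and 6.2.6 describes the on-treatment subset, so it does not conflict with run-in events being TEAEs.

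**What to change.** In SAP 6.7.1:
- Base the by-arm serious, fatal and leading-to-death rows and tables on the on-treatment definition (onset or worsening after the first randomized dose), so that the fatal table matches its listing.
- Keep run-in events in their separate listing, and label the all-TEAE row as including the run-in if it is retained.
- State one end day that applies to both new and worsened events. Choose it, or add a by-arm row for later events, so that SAEs and deaths collected up to 30 days (Part 1) or 15 days (Part 2) are not lost from the by-arm serious and fatal tables.

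In SAP 6.2.6, make the flag match the 6.7.1 on-treatment definition, including worsening of events that began before Randomization and the same anchor.

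The cost is SAP text and a small programming change that re-uses a flag already planned. No new data are needed, and the protocol's statement that run-in AEs are treatment-emergent can stand. A few late events may be added to the tables.

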6.7.1.1 Adverse Events of Special Interest (AESI)

The AESIs for all study drugs (MLS-101 and placebo) include the following:

- Hyperkalemia with dose modification (dose reduction, dose hold, or permanent dose withdrawal),
- Hypotension with symptoms (eg, light-headedness, dizziness, presyncope, or syncope),
- Adrenal Insufficiency.

If AESI are reported in the eCRF these will be prioritized and used for all analyses. Otherwise, the above definition of AESI will be used.

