## 1. SYNOPSIS

Name of Sponsor/Company: Mineralflys Therapeutics, Inc.	
Name of Investigational Product: MLS-101: [REDACTED] [REDACTED]	
Name of Active Ingredient: MLS-101	
Title of Study: A Randomized, Double-blind, Placebo-controlled, Dose-ranging, Multicenter Phase 2 Study to Evaluate the Safety, Efficacy, and Tolerability of MLS-101 in Subjects With Uncontrolled Hypertension	
Number of Study Center(s): Approximately 50 centers in the United States for Part 1 and approximately 10 centers in the United States for Part 2	
Study Period: Date first subject enrolled: 30 July 2021 Estimated date last subject last visit: Q3 2022	Phase of Development: Phase 2
Objectives and Endpoints: Objectives: Primary: 

To characterize the effect of MLS-101 on blood pressure (BP) at 5 dosing regimens versus placebo when administered orally for the treatment of uncontrolled hypertension as add-on therapy to stable background treatment

 Secondary: 

To investigate the safety and tolerability of MLS-101 at 5 dosing regimens versus placebo when administered orally for the treatment of uncontrolled hypertension as add-on therapy to stable background treatment

To investigate the pharmacokinetic (PK) profile of MLS-101 at 5 dosing regimens when administered orally for the treatment of uncontrolled hypertension as add-on therapy to stable background treatment

To investigate the pharmacodynamic (PD) parameters of MLS-101 at 5 dosing regimens when administered orally for the treatment of uncontrolled hypertension as add-on therapy to stable background treatment

 Endpoints: Efficacy Primary: 

Change in office-measured (average of last 2 of 5 unattended measurements using an automated oscillometric sphygmomanometer device after approximately 5 minutes of rest in the seated position) systolic blood pressure (SBP) from baseline to the end of Study Week 8 (ie, Study Day <math>56 \pm 2</math> or end-of-treatment period)

 Secondary: 

Change in 24-hour ambulatory blood pressure monitoring (ABPM) parameters (systolic and diastolic) from baseline to the end of Study Week 7 (ie, Study Day <math>49 \pm 2</math>)

	

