A planned interim analysis ([Section 9.5](#)) was conducted for Part 1 of the study and all available safety and tolerability data (vital signs, BP measurements, adverse events, and safety laboratory values) were reviewed by a Data and Safety Monitoring Board (DSMB) ([Section 8.3.8](#)). A second interim analysis at the end of Part 1 to review all available safety and tolerability data (vital signs, BP measurements, adverse events, and safety laboratory values) will be conducted. This analysis will also include Part 2 subjects that have completed week 4 at the time of data cut off. An additional interim analysis may be performed to support drug development decisions.

NOTE: In the previous version of the protocol, subjects in Part 1 of the study were randomized into 6 equal treatment groups (1:1:1:1:1:1) to 12.5 mg BID, 25 mg BID, 12.5 mg QD, 50 mg QD, 100 mg QD, or placebo. After a review of the clinical data at the December 2021 interim analysis, it was decided that the 2 lowest dose levels (12.5 mg QD and 12.5 mg BID) would be dropped due to lack of consistent meaningful reduction of blood pressure. Effective with Amendment 4, subjects will be randomized into 4 equal treatment groups (1:1:1:1) to 25 mg BID, 50 mg QD, 100 mg QD, or placebo.

For Part 1, approximately 120 of 160 enrolled subjects  $\geq$  18 years of age will be randomized into 4 equal treatment groups (1:1:1:1) to 25 mg BID, 50 mg QD, 100 mg QD, or placebo; each treatment group will consist of approximately 30 subjects stratified by BP (seated SBP  $\leq$  160 mmHg and seated SBP  $>$  160 mmHg). Approximately 40 of 160 enrolled subjects were enrolled and completed the study in the 2 low dose cohorts that were discontinued with Amendment 4 as described above.

For Part 2, approximately 36 enrolled subjects  $\geq$  18 years of age will be randomized (5:1) to either 100 mg QD MLS-101 or placebo such that the MLS-101 treatment group will consist of approximately 30 subjects and the placebo treatment group will consist of approximately 6 subjects.

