### **8.3.7. Adverse Events of Special Interest**

Adverse events of special interest (AESI) are required to be reported by the investigator to the sponsor/designee immediately (ie, no more than 24 hours after learning of the event) regardless of their causality to the study drug treatment. The most appropriate diagnosis should be recorded, or if a diagnosis cannot be established, the abnormal laboratory values should be recorded on the safety event report form and reported to the sponsor/designee immediately, either as an AESI or and/or a SAE.

NOTE: If any of the following events were reported as SAEs then there is no need to complete a separate AESI form.

The AESIs for all study drugs (MLS-101 and placebo) include the following:

- Hyperkalemia with dose modification (dose reduction, dose hold, or permanent dose withdrawal)
- Hypotension with symptoms (eg, light-headedness, dizziness, presyncope, or syncope)
- Adrenal Insufficiency

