### 12.11.3. Amendment 4 (10 January 2022)

This summary includes changes made to Protocol MLS-101-201 Amendment 3 (24 August 2021). The overall rationale for the changes implemented in this protocol amendment was to reduce the number of cohorts from 6 to 4 by stopping enrollment into the 2 low dose cohorts (12.5 mg QD and 12.5 mg BID). This decision was based on a review of the clinical data at the December 2021 interim analysis. In addition, the ABPM procedure is now initiated at the end of Study Week 7 instead of Study Week 8 to allow for it to be repeated at Study Week 8 if deemed a failure at Study Week 7.

The following is a summary of content-oriented changes that were made to each section of the protocol, and a brief rationale for these changes. Minor editorial and document formatting revisions have not been summarized.

Section/Section Title	Description of Change (strikeout denotes a deletion; bold denotes an addition)	Brief Rationale for Change
Synopsis/Endpoints and 3.2.2/ Secondary Efficacy Endpoints	Change in 24-hour ambulatory blood pressure monitoring (ABPM) parameters (systolic and diastolic) from baseline to the end of Study Week 87 (ie, Study Day <del>5649 ± 2 or end of treatment period</del> )	To allow for the ABPM procedure to be repeated at Study Week 8 if deemed a failure at Study Week 7
Synopsis/Methodology and Section 4.1/Overall Study Design and Synopsis/Eligibility Criteria and Section 5.1/Inclusion Criteria (#5 and #6)	The value for PRA will not exceed 0.61 ng/mL based on morning measurement. The value for aldosterone will not be less than <del>61</del> ng/dL based on morning measurement.	To clarify the qualifying PRA and serum aldosterone levels required at prescreening for eligibility

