Section 6.3/Randomization and Blinding	
...will be randomized into <del>64</del> equal treatment groups (1:1:1:1:1:1) to <del>12.5 mg BID, 25 mg BID, 12.5 mg once daily (QD), 50 mg QD, 100 mg QD, or placebo;</del>
	To clarify that subjects will no longer be enrolled into the 2 low dose cohorts
Section 6.5.1/Hyperkalemia/Table 2	
Modified table to remove the 2 low dose cohorts (12.5 mg BID and 12.5 mg QD)
	To remove the 2 low dose cohorts
Section 8.1.2/24-hour Ambulatory Blood Pressure Monitoring	
Subjects will be monitored by ABPM for 24 hours before the first dose on Study Day 1 and <del>after</del>before the <del>last</del>first dose on Study Day <del>5649</del> <math>\pm</math> 2 days (end of Week 87)... The ABPM procedure will be initiated at home approximately 24 hours before Randomization (Study Day 1) and again at the Study Week 87 visit (ie, Visit 4413; Study Day <del>5649</del> <math>\pm</math> 2 <del>or end of treatment period</del>).
 
Alternatively, sites may choose to schedule an office visit on Study Day 0 (Visit 5) to initiate the ABPM procedure (the ABPM procedure will be initiated in the clinic at Study Week 87 unless a subject is not able to attend the visit due to extraordinary circumstances, such as COVID-19 restrictions including site closure, subject exposure to COVID-19, or subject testing positive for COVID-19). If, for any reason, the ABPM procedure is deemed a failure at the end of Study Week 7, it can be repeated at Study Week 8.
	
 
• To clarify that ABPM will be initiated at the end of Study Week 7 instead of Study Week 8
 
• To add language to account for deviations in study conduct due to COVID-19
 
• To allow for the ABPM procedure to be repeated at Study Week 8 if deemed a failure at Study Week 7
 

Section 8.3.7/Adverse Events of Special Interest	
Hyperkalemia with dose modification (dose reduction, dose hold, or permanent dose withdrawal)
	To update based on new guidance that hyperkalemia will be considered an AESI if it requires dose modification

Section/Section Title	Description of Change (strikeout denotes a deletion; bold denotes an addition)	Brief Rationale for Change

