Section 8.2.4/Electrocardiogram	<del>These ECG readings will be sent to a core ECG laboratory for central review. Any abnormalities observed at Screening will be reported to the investigator to assist in Inclusion/Exclusion evaluations.</del>	Deleted ECG central lab review
Section 8.3.1/Time Period and Frequency for Collecting AE and SAE Information	<del>Medical occurrences Adverse events that begin before the start of study drug, but after obtaining informed consent will not be recorded as medical history/current medical conditions, not as treatment-emergent AEs. Adverse events collected during Placebo Run-in are not considered treatment-emergent events for the purposes of data analyses.</del>	Clarified timing of collection of adverse events
Section 8.3.7/Adverse Events of Special Interest	The AESIs for all study drugs ( MLS-101 and placebo ) include the following: 
 
Hyperkalemia
 
Hypotension with symptoms (eg, light-headedness, dizziness, presyncope, or syncope)
 
Adrenal Insufficiency
 
	Clarified definition of study drugs and added adrenal insufficiency as an AESI
Section 8.4/Pharmacokinetics	<del>...on Study Day 1 (predose), and at Study Weeks 1, 4, and 8 (trough levels). Additional blood samples for long-term storage for metabolites, drug-drug interaction profiles of background therapy, or other exploratory analyses will also be collected at baseline (predose) and at Study Weeks 1, 4, and 8.</del>	Added additional PK sample collection at Study Week 8 and clarified that additional blood samples will also be collected at these time points
Section 8.5/Pharmacodynamics	Blood plasma samples for aldosterone, cortisol , 11-deoxycorticosterone, 11-deoxycortisol, and PRA will be collected at Screening, Study Day 1 (baseline), Study Week 4, and Study Week 12 (end of follow up).	Added cortisol to pharmacodynamic measurements
Section 9.3.3/Safety Analyses	The safety analysis set will be used for the efficacy/safety analyses.	Corrected typo

Section/Section Title	Description of Change (strikeout denotes a deletion; bold denotes an addition)	Brief Rationale for Change

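### SAP 6.7.1.1 ranks eCRF-reported AESIs above the stated definition, so hyperkalemia AESI counts may mix a broad and a narrow definition across enrolment periods

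*SAP*

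**What the plan says.** SAP 6.7.1.1 lists three AESIs in the words of the current protocol. The first, as in Protocol 8.3.7, is "Hyperkalemia with dose modification (dose reduction, dose hold, or permanent dose withdrawal"). The SAP then sets the source of the data: "If AESI are reported in the eCRF these will be prioritized and used for all analyses". The fallback is "Otherwise, the above definition of AESI will be used". It does not say whether the fallback works per event, per subject or for the whole study.

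The protocol's amendment history shows which definition sites were given, and when. Under Amendment 1 the item was simply "Hyperkalemia". The summaries of Amendments 2 and 3 list no change to Section 8.3.7. Amendment 4 narrowed the item, with the reason "To update based on new guidance that hyperkalemia will be considered an AESI if it requires dose modification". The synopsis gives "Date first subject enrolled: 30 July 2021", so recruitment had run for about five months by then.

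Amendment 4 also closed the two 12.5 mg arms: "Approximately 40 of 160 enrolled subjects were enrolled and completed the study in the 2 low dose cohorts" (Protocol synopsis, Methodology). Part 2 was added later, by Amendment 5 (17 February 2022).

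SAP 2.1 keeps all six treatment groups in the presentation. SAP 6.7.1 tabulates AESIs by treatment group and for pooled active treatment, both in the overall summary and by system organ class and preferred term.

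**The concern.** The issue is not that an amendment log differs from the current text. The log matters here because it shows which rule governed the flags when they were entered. A rule that takes the flag first carries both definitions into one table. An early hyperkalemia event without a dose change can be counted as an AESI while an identical later event is not.

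Enrolment period is tied to treatment group for the two dropped arms, and to Part. If the flags followed the rule in force, the lowest doses would be counted on the more generous definition. That pushes towards flattening any dose relation in hyperkalemia AESIs, in a dose-ranging trial of a mechanism that the protocol's benefit/risk section says may cause hyperkalemia.

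**Working it through.** **Enrolment split.** The plan's figures are 4 continuing Part 1 arms of about 30, and about 40 subjects in the two 12.5 mg arms (Protocol synopsis, Methodology). 4 × 30 + 40 = 160, which reproduces the stated Part 1 total.

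Allocation before Amendment 4 was equal across six arms. The 40 low-dose subjects mean about 20 per arm, so about 20 had also been randomized to each of the other four arms. Share randomized under the broad definition:

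- 12.5 mg QD and 12.5 mg BID: about 100%
- 25 mg BID, 50 mg QD, 100 mg QD and Part 1 placebo: w = 20/30, about 67% (53% to 80% if the low-dose arms held 16 to 24 each)
- Part 2: 0%

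These shares go by randomization date. Subjects on study when the amendment took effect had time under both definitions, which would blur the split.

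**Counted rates.** Let h be the true proportion with a hyperkalemia AE, set equal everywhere, and f the share of those events with a dose modification. The documents do not give f, so a range is shown. Assume each flag followed the definition in force at randomization and was not revised. Then:

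- 12.5 mg arms: h
- continuing Part 1 arms, including placebo: h × c, with c = w + (1 − w)f
- Part 2: h × f
- Part 1 pooled active (40 low-dose plus 90 continuing subjects): h × (40 + 90c)/130

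Artificial ratios with w = 2/3:

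| f | c | 12.5 mg vs continuing arm, 1/c | Part 1 pooled active vs placebo, (40 + 90c)/(130c) | Part 1 vs Part 2 at 100 mg, c/f |
|---|---|---|---|---|
| 0.25 | 0.750 | 1.33 | 1.10 | 3.00 |
| 0.50 | 0.833 | 1.20 | 1.06 | 1.67 |
| 0.75 | 0.917 | 1.09 | 1.03 | 1.22 |
| 0.90 | 0.967 | 1.03 | 1.01 | 1.07 |

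Among the four continuing Part 1 arms the ratio is c/c = 1.00 whatever f is. Over w = 0.5 to 0.8 and f = 0.25 to 0.90, the low-dose ratio runs from 1.02 to 1.60 and the Part 1 to Part 2 ratio from 1.06 to 3.40.

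**In subjects.** For illustration take h = 10% and f = 0.50. A 12.5 mg arm of 20 would show 20 × 0.10 = 2.0 subjects, against 20 × 0.10 × 0.833 = 1.67 on the continuing-arm mix, a difference of a third of a subject. At 100 mg, 30 subjects would show 2.5 in Part 1 and 1.5 in Part 2.

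**The case against.** The strongest reply is that little of consequence is exposed. Most of it stands.

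- **Main randomized contrasts.** The three retained doses and Part 1 placebo were randomized concurrently and equally before and after Amendment 4, so they share one mix of definitions. A reader might infer that the active-versus-placebo comparisons at those doses are biased. They are not.
- **Parts.** A reader might infer that both Parts go into one AESI table. SAP 5.3 summarizes them separately. Only Protocol 9.3.3 sets them side by side, in selected safety summaries at 100 mg by PRA cohort, and it does not say that AESIs are among those selected. That comparison is in any case not randomized, and the potassium entry limits differ: exclusion above 5.2 mEq/L in Part 1 and above 4.8 mEq/L in Part 2.
- **A hidden safety signal.** A reader might infer that the rule can conceal a dose relation in hyperkalemia. Several planned outputs do not use the flag: on-treatment TEAEs by preferred term and arm, TEAEs leading to dose modification, the listing of all AEs, and the potassium shift table and plots (SAP 6.7.1 and 6.7.2.1).
- **Size.** Protocol 6.5.1 calls for a dose reduction or hold when potassium above 5.2 mEq/L is confirmed locally, and an immediate hold above 6. That points to a high f and to the bottom rows of the table. It does not make f equal to 1: an event not confirmed on retest, or first found at the Week 8 visit, may involve no dose change.
- **Flag practice.** The eCRF and its completion rules are not in the documents. The SAP v2.0 change list mentions a clarification of how AESIs are identified, without saying how. Early flags may have been reconciled, or reported AESIs may be meant as those meeting the list just above. This makes the concern conditional. It does not remove it, because the text as written still ranks the flag above the definition.
- **SAP section 7.** That section lists differences between protocol and SAP. The two agree on the current definition, so the omission there is not itself an error.

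**Conclusion.** The rule is inconsistent with a definition that changed during the trial, and neither document ensures that one definition applies to every subject. The effect is confined to three places: the 12.5 mg arms against the others, the Part 1 pooled-active column against placebo, and any 100 mg AESI summary by PRA cohort.

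At the higher values of f, which Protocol 6.5.1 makes more plausible, the distortion is small: at f = 0.75 to 0.90, 1.09 to 1.03 for the 12.5 mg arms and 1.22 to 1.07 for Part 1 against Part 2. It is larger only if few hyperkalemia events led to a dose change. All these figures assume equal true risk, flags that followed the definition in force at randomization, no later reconciliation, and w of about two thirds. The documents establish neither f nor the flag practice.

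This is a low-cost consistency fix. The documents do not support reading it as a serious threat to the safety conclusions.

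**What to change.** In SAP 6.7.1.1, replace the flag-first rule for hyperkalemia with one derivation for every subject under the current definition: AE term plus action taken with study drug or the dosing record, whatever the eCRF flag says. List events where flag and derivation disagree, with the protocol version in force at the time. State in the SAP that the definition changed with Amendment 4; a line beside the ABPM timing note in section 7 would do. A separate row for all hyperkalemia AEs is optional, because the preferred-term table already shows them.

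With one definition applied to every subject, the artificial ratio is 1.00 for every contrast. The cost is a few lines of SAP text, a small derivation and one listing. No new data are needed: SAP 6.7.1 already tabulates TEAEs leading to dose modification, and SAP 6.3.5 already lists the reasons for modification.
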